4.1.2 Exclusion Criteria

1. Allogenic bone marrow transplant within 12 months prior to the first dose of BI-1206 or presence of chronic graft versus host disease.
2. Patients with clinically active leptomeningeal or central nervous system lymphoma/leukaemia.
3. Patients who receive doses of prednisolone >10 mg daily (or equipotent doses of other corticosteroids) are not eligible for the study unless administered as pre-medication.
During the screening period, doses of up to 20 mg per day may be given but the dose must be reduced to 10 mg/day by Week 1 Day 1. See Sections 5.9.2 and Section 5.10 regarding allowable pre-medication and conditions for steroid use
4. Known or suspected hypersensitivity to study drugs.
5. Cardiac or renal amyloid light-chain (AL) amyloidosis.
6. Patients who have received radiotherapy, endocrine therapy*, immunotherapy, chemotherapy or investigational medicinal products during the previous 4 weeks before treatment, must discuss with the CI and Sponsor to agree the appropriate interval (if required) between prior therapy and commencement of BI-1206. The wash out duration will be compatible with the clinical context within which previous medication had been used. Patient must also have recovered from therapy related toxicity.
* exceptions to endocrine therapy are noted in exclusion criteria #13 and #19.
7. Ongoing toxic manifestations of previous treatments. Exceptions to this are alopecia or certain \leq Grade 2 toxicities, which in the opinion of the Investigator and the Sponsor should not exclude the patient.
8. Ability to become pregnant (or already pregnant or lactating). However, those female patients who have a negative serum or urine pregnancy test before enrolment and agree to use two forms of contraception (one highly effective form plus a barrier method) [oral, injected or implanted hormonal contraception and condom; intra-uterine device and condom; diaphragm with spermicidal gel and condom] or agree to sexual abstinence⁴, for four weeks before entering the trial, during the trial and for twelve months after completing treatment are considered eligible.
9. Male patients with partners of child-bearing potential (unless they agree to take measures not to father children by using a barrier method of contraception [condom plus spermicide] or to sexual abstinence effective from the first administration of BI-1206 or rituximab on the study, throughout the trial and for twelve months afterwards. Men with partners of child-bearing potential must also be willing to ensure that their partner uses an effective method of contraception for the same duration for example, hormonal contraception, intrauterine device, diaphragm with spermicidal gel or sexual abstinence⁴). Men with pregnant or lactating partners should be advised to use barrier method contraception (e.g. condom plus spermicidal gel) to prevent exposure to the foetus or neonate.
10. Major thoracic or abdominal surgery from which the patient has not yet recovered.
11. At high medical risk because of non-malignant systemic disease including infection.
12. Known to be serologically positive for hepatitis B, hepatitis C (hepatitis C antibody positive patients are eligible providing PCR for viral RNA is negative) or human immunodeficiency virus (HIV).

⁴ Abstinence is only considered to be an acceptable method of contraception when this is in line with the preferred and usual lifestyle of the subject. Periodic abstinence (e.g., calendar, ovulation, symptothermal, post-ovulation methods) and withdrawal are not acceptable methods of contraception.

13. Patients with an active⁵ autoimmune disease (not including CLL auto-immune disease). Patients with Type I diabetes mellitus, hypothyroidism only requiring hormone replacement, skin disorders (such as vitiligo, psoriasis, or alopecia) not requiring systemic treatment, or conditions not expected to recur in the absence of an external trigger will be permitted to participate.
14. Concurrent congestive heart failure, prior history of class III/ IV cardiac disease (New York Heart Association [NYHA] Section 16.3 Appendix 3), history of clinically significant cardiac ischaemia or clinically significant history of cardiac arrhythmia in the past 6 months.
For events that are deemed to be not clinically significant and have occurred in the last 6 months, Investigator must discuss with CI and Sponsor to confirm eligibility.
15. Patients for whom rituximab is contraindicated due to severe previous hypersensitivity or any other reason (Arm 2 in Parts A & B [combination arms] only).
16. Ongoing infection requiring treatment with antibiotics, antifungals or antivirals. Prophylactic use of antibiotics, antifungals or antivirals will not exclude patients.
17. Any other condition which in the Investigator's opinion would not make the patient a good candidate for the clinical trial.
18. Is a participant or plans to participate in another interventional clinical study, whilst taking part in this Phase I/IIa study of BI-1206. Participation in an observational study would be acceptable.
19. Current malignancies of other types, with the following exceptions:
 - Adequately treated cone-biopsied *in situ* carcinoma of the cervix uteri and basal or squamous cell carcinoma of the skin.
 - Asymptomatic prostate cancer without known metastatic disease, with no requirement for therapy or requiring only hormonal therapy (either past or continuing) and with normal prostate-specific antigen for ≥ 1 year prior to start of study therapy are eligible for the trial.
 - Current or prior malignancy which could affect compliance with the protocol or interpretation of results. Patients with curatively-treated non-melanoma skin cancer, non-muscle-invasive bladder cancer, or carcinomas-in-situ are generally eligible.

4.2 Patient enrolment

Before enrolling the patient in the trial, the Investigator or designated representative should determine the eligibility of the patient during the trial screening period.

Eligible patients must be enrolled in the electronic data capture (EDC) system by site staff and then registered by the CDD before they start treatment with BI-1206 \pm rituximab. Eligible patients will be allocated a study number by the EDC system during the enrolment process. The CDD will send confirmation of the patient registration, including the assigned dose level and assigned treatment arm (single agent or combination), to the Investigator following enrolment of the patient. Study treatment may only be administered after this confirmation has been received.

⁵ History of autoimmune disease, including but not limited to myasthenia gravis, myositis, autoimmune hepatitis, systemic lupus erythematosus, rheumatoid arthritis, inflammatory bowel disease, vascular thrombosis associated with antiphospholipid syndrome, Wegener's granulomatosis, Sjögren's syndrome, Guillain-Barré syndrome, multiple sclerosis, vasculitis, or glomerulonephritis (Patients with a history of autoimmune-related hypothyroidism on a stable dose of thyroid replacement hormone will be eligible as will be patients with controlled Type I diabetes mellitus on a stable dose of insulin). Patients with eczema, psoriasis, lichen simplex chronicus, or vitiligo with dermatologic manifestations only (e.g., patients with psoriatic arthritis are excluded) are eligible for the study provided all of following conditions are met:

- Rash must cover $< 10\%$ of body surface area
- Disease is well controlled at baseline and requires only low-potency topical corticosteroids
- No occurrence of acute exacerbations of the underlying condition requiring psoralen plus ultraviolet A radiation, methotrexate, retinoids, biologic agents, oral calcineurin inhibitors, or high-potency or oral corticosteroids within the previous 12 months

5 TREATMENT

5.1 Selection of the Phase I starting dose and schedule

5.1.1 Rationale for starting dose BI-1206 and rituximab

BI-1206 (single agent) will be given at a starting dose of 0.4 mg, please refer to Section 2.3.1 for rationale.

The BI-1206 dose levels are flat doses given in units of mg for each cohort, whereas the rituximab doses are adjusted for the body surface area (BSA) of each patient and given in units of mg/m².

The dose(s) of rituximab used in Part A & B of the study will be a fixed dose of 375 mg/m² based upon the approved dose of rituximab.

For the purpose of this trial, all patients including CLL will receive 375 mg/m² for every rituximab infusion for consistency. The proposed weekly dosing schedule with BI-1206 and rituximab is in line with the rituximab SmPC standard of care for patients who receive rituximab alone. The 8 weekly maintenance therapy schedule is at a frequency in line with rituximab administration post chemotherapy and will only be given if patients are showing clinical benefit as defined in Section 10.2.

Single agent BI-1206 (Arm 1) will be initiated first in Part A and BI-1206 in combination with rituximab (Arm 2) may start once the intrapatient dose escalation cohort (Cohort 1) in Arm 1 has been completed.

The starting dose level for BI-1206 in Part A, Arm 2 will not exceed the highest dose of BI-1206 that has been safely given as a single agent in Part A, Arm 1 and deemed safe to be given in combination, following review in the Dose Decision Meeting (see Section 5.3). This will allow assessment of any single agent BI-1206 toxicity at the specified dose level to decide if it would be clinically appropriate to start the combination arm (Part A, Arm 2)

Once the combination dose escalation arm (Arm 2) is opened, both arms will run in parallel but independently, to determine RP2D of single agent BI-1206 in Part A, Arm 1 and RP2D of BI-1206 in combination with rituximab in Part A, Arm 2 (see Sections 5.4 and 5.5).

The RP2D of BI-1206 in the relevant arm (single agent or combination) needs to be established in Part A before the respective expansion cohort in Part B of the trial opens to recruitment (single agent expansion cohort, Arm 1 and combination expansion cohort, Arm 2, see Sections 5.7 and 5.8). Arm 1 and Arm 2 in Part B may open and progress independently of each other.

5.2 Dosing schedule/treatment schedule

5.2.1 Dosing schedule/treatment schedule in BI-1206 single agent escalation phase (Part A, Arm 1)

BI-1206 will be administered once weekly for four weeks, this will be classified as induction therapy. The starting dose of BI-1206 will be 0.4 mg given as a 30 minute (min) intravenous (IV) infusion. Intra-patient dose escalation will be performed in the first cohort which will consist of a minimum of one patient. In Cohort 1, if a patient withdraws before completing induction therapy for reasons other than DLT they will be replaced, following a dose review meeting at which the planned dose level for the replacement patient will be decided (the starting dose for this patient will be at or below a level already received on the study, see Section 5.4).

Subsequent cohorts will be at doses that are approximately comparable to or above the expected pharmacologically active dose (PAD) determined based on the preclinical toxicology data (>60 mg). These cohorts will include a minimum of one patient cohorts as described in Section 5.4. The maximum weekly dose of BI-1206 to be administered will be 800 mg, infusion times will vary dependent on the

dose administered. Patients with clinical benefit at eight weeks (as defined in Section 10.2) will move to a maintenance phase of treatment. Refer to Section 5.2.5.

5.2.2 Dosing schedule/treatment schedule in BI-1206/rituximab combination escalation phase (Part A, Arm 2)

BI-1206 and rituximab will each be administered once weekly for four weeks via separate IV infusions. Based on the proposed mechanism of action of BI-1206 binding to the CD32b receptor and blocking its ability to internalise rituximab, BI-1206 will be administered prior to rituximab. The timeframe within which the two infusions can be given (i.e. on the same day or on subsequent days) will be determined by the length of each infusion. At Week 1 both infusions will be administered over a longer period of time as a precautionary measure and so the BI-1206 dose will be given on Day 1 and the rituximab dose on Day 2. In subsequent weeks, if patients have not experienced a significant infusion reaction at Week 1 then the BI-1206 and rituximab infusions can be given at a faster rate. Therefore, from Week 2 onwards, if the infusion times allow, the doses of BI-1206 and rituximab may be given on the same day. BI-1206 will be given prior to rituximab on all occasions. If infusion times are not compatible with same-day dosing, administration of BI-1206 and rituximab on subsequent days will continue. These cohorts will include a minimum of one patient as described in Section 5.5.

Patients who show clinical benefit at eight weeks (as defined in Section 10.2) will move to a maintenance phase of treatment (refer to Section 5.2.5).

Figure 3: Combination dosing schedule during induction therapy

	Week 1				Week 2				Week 3				Week 4			
	D1	D2	D3	D4	D8	D9	D10	D11	D15	D16	D17	D18	D22	D23	D24	D25
BI-1206	X				X				X				X			
Rituximab			X		X ¹				X ¹				X ¹			

¹ Rituximab may be given on Day 1 following BI-1206 from Week 2 onwards if no significant infusion reaction has been observed at Week 1 and if infusion times allow this.

Otherwise it will be given on Day 2 as in Week 1.

5.2.3 Dosing schedule/treatment schedule in BI-1206 single agent expansion phase (Part B, Arm 1)

BI-1206 will be administered once weekly for four weeks via IV infusion at the RP2D as defined by Part A, Arm 1 this will be classified as induction therapy; refer to Section 5.7. Patients with clinical benefit (as defined in Section 10.2) at eight weeks will move to a maintenance phase of treatment as described in Section 5.2.5.

5.2.4 Dosing schedule/treatment schedule in BI-1206/rituximab combination expansion phase (Part B, Arm 2)

BI-1206 and rituximab will each be administered once weekly for four weeks via separate IV infusions. BI-1206 will be administered at the RP2D as defined in Part A, Arm 2 and rituximab at the fixed dose of 375 mg/m²; this will be classified as induction therapy, refer to Section 5.8. Patients with clinical benefit (as defined in Section 10.2) at eight weeks will move to a maintenance phase of treatment as described in Section 5.2.5.

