Patients who are to receive rituximab (Arm 2 in Parts A and B): For those patients whose lymphocyte counts are $>25 \times 10^9/L$ it is recommended to administer prednisone/prednisolone 100 mg IV shortly before rituximab infusion to decrease the rate and severity of acute infusion reactions and/or CRS. A reduced infusion rate should be considered for these patients for the first infusion and a split dosing over two days during the first week, i.e. rituximab 100mg IV Day 1 (Week 1 only) followed by rituximab 375mg/m² minus 100mg IV Day 2 (Week 1 only). The rate of infusion and confirmation of split dosing in subsequent weeks must be agreed with the Sponsor and CI prior to commencement of treatment.

Patients who are to receive BI-1206 (All patients): If IRRs are seen following Week 1 infusion, the Investigator may consider split dosing over 2 days for subsequent infusions (from Week 2 onwards) to decrease severity of reactions in subsequent doses. The rate of infusion and confirmation of split dosing must be agreed with the Sponsor and CI prior to commencement of treatment.

Patients with severe, life threatening reactions to BI-1206 or rituximab must not receive further infusions and should be withdrawn from the trial.

Investigators have the option to split the dose of BI-1206 at any point from (and including) Week 1 onwards based on clinical presentation of the patient at study entry and the Investigator's clinical judgement of what is likely to be most appropriate for an individual patient and collective study experience with giving BI-1206 to date. Once the decision to split a dose is taken, the patient must continue to receive split dosing for the duration of their study participation.

For rituximab, as per normal clinical practice, Investigators have the option to revert back to single dosing after splitting the dose.

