6.2.11 Rituximab administration

Before administration, the exact dosage must always be double-checked by a second suitably qualified person. All checks and double-checks must be documented (signed and dated) and the documentation must be available for the CRA/CSM to verify.

Rituximab will be administered at the following rates (as per the SmPC specific to the brand being used).

First infusion

The initial rate for infusion is 50 mg/h; after the first 30 minutes, it can be escalated in 50 mg/h increments every 30 minutes, to a maximum of 400 mg/h.

For those patients whose lymphocyte counts are $>25 \times 10^9/L$, a reduced infusion rate should be considered for the first infusion and dosing may be split over two days during the first week, i.e. rituximab 100mg IV Day 1 (Week 1 only) followed by rituximab 375mg/m² minus 100mg IV Day 2 (Week 1 only). The Sponsor and CI must agree the required infusion rate and any split dosing requirements and communicate these to the investigator site before the start of treatment.

Subsequent infusions

Subsequent doses can be infused at an initial rate of 100 mg/h, and increased by 100 mg/h increments at 30 minute intervals, to a maximum of 400 mg/h.

Patients with severe, life threatening reactions to rituximab must not receive further infusions and should be withdrawn from the study.

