(h) For patients recruited to Part A & B, Arm 2, rituximab to be given on Day 2 post BI-1206 at Week 1. If infusion time permits, then subsequent doses of rituximab will be given on the same day as BI-1206. Maintenance treatment (from Week 8) will only be given if a patient is deemed eligible to continue on to maintenance treatment following Week 8 assessments.

If split dosing is implemented, laboratory tests will be relative to the first infusion administered each week then as clinically indicated on the second day.

(i) Maintenance therapy will only be given to those patients who demonstrate stable or responding disease and will start after the Week 8 scan results following induction therapy confirming patient is eligible for maintenance treatment. Patients will receive the same dose of BI-1206 (and rituximab if received) as in their induction therapy from week 8 onwards (i.e. Week 9 or 10) and every 8 weeks (\pm 2 weeks) from the first maintenance dose, for up to one year from first induction dose.

(j) A CT scan to assess the patient's tumour burden to be performed at Week 8 (prior to commencing maintenance therapy) and then every 16 weeks (\pm 2 weeks) during maintenance therapy and at off-study. Patients with Waldenstrom's macroglobulinaemia will also have serum paraprotein samples taken at these time points. If a complete response is noted, a bone marrow biopsy may be performed and in a lymphoma patient with PET-avid disease a FDG-PET scan will also be performed. A scan is only required at Off-study if no appropriate disease assessment has been performed recently (at week 8 or as required on maintenance).

(k) Monthly follow-up required ONLY for those AEs and SAEs considered drug-related (highly probable, probable or possible) and present at off-study. Monthly follow-up for AEs to continue until resolution, return to baseline, stabilisation or patient starts another anti-cancer treatment.

(l) Day 11, 18, 25 assessments performed for patients in Cohort 1, Arm 1 only.

(m) Bone marrow aspirate samples are used for pharmacodynamic analysis, trephine samples are to be taken where required for disease assessment, if a sample is taken as part of routine care within 8 weeks prior to starting on the study a repeat baseline sample is not required. After baseline, a bone marrow sample is only required for disease assessment to confirm at complete response.

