8.3.1.3 Pharmacokinetic sampling, Part A & B, Arm 2 (BI-1206 plus rituximab)

For patients receiving **combination therapy with BI-1206 and rituximab in the Part B Arm 2 expansion**: a 6 mL blood sample will be taken pre- BI-1206 infusion, at the end of the BI-1206 infusion (+5 mins), 4 hours after the end of the BI-1206 infusion (\pm 15 mins), at 24 hours after the BI-1206 infusion (before the rituximab infusion) and at 72 hours after the BI-1206 infusion at Week 1. Samples will also be taken pre- BI-1206 infusion at Weeks 2 and 3. At Week 4, samples will be taken prior to the BI-1206 infusion, at the end of the BI-1206 infusion, 4 hours after the BI-1206 infusion (or if rituximab is given on the same day, at the end of rituximab infusion), at 24 hours after the BI-1206 infusion (before the rituximab infusion) and at 72 hours after the BI-1206 infusion. During the maintenance period, a sample will be taken prior to each BI-1206 infusion. The approximate volume of blood withdrawn from each patient in the Part B expansion be 72 mL during the induction period with an additional 36 mL withdrawn over the subsequent maintenance treatment period (Table 5).

Table 5: Parts A & B Arm 2, combination PK sampling schedule

Time	Induction				Maintenance
	Week 1	Week 2	Week 3	Week 4	
Pre	X	X	X	X	X
EOI (BI-1206)	X			X	
+ 4hrs (BI-1206)	X			X ^	
+ 24hrs (BI-1206)	X			X	
+72hrs (BI-1206)	X			X	
Total (mL)	72				(up to 36)

[^] If rituximab is given on Day 1, this sample will be at the end of rituximab infusion instead

For split dosing administration of BI-1206 plus rituximab:

- Up to 18 PK time points may be taken during the induction period (8 weeks) with an additional 6 PK timepoints thereafter (to include pre-infusion sampling during the maintenance phase). This will be approximately 108 mLs taken over the first eight weeks with approximately 36mLs taken post the induction phase, throughout the maintenance phase.
- If split dosing is implemented, the blood volume requested may increase from 72 mL to 108 mL, over the first eight weeks.
- Please refer to the study laboratory manual for handling, adjusted sample times, sample volume per time point, storage and shipment of samples.

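### Arm 2, Week 1: the optional rituximab split for high lymphocyte counts is printed as starting on Day 1, although 5.2.2 and schedule note (h) put rituximab on Day 2

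*Combined protocol and SAP*

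**What the plan says.** Section 5.2.2 (combination escalation) runs both Week 1 infusions slowly "as a precautionary measure and so the BI-1206 dose will be given on Day 1 and the rituximab dose on Day 2". From Week 2 the two may share a day if there was no significant Week 1 reaction and infusion times allow. Note (h) in Section 7.6 covers Arm 2 in Parts A and B: "rituximab to be given on Day 2 post BI-1206 at Week 1", and then "If infusion time permits, then subsequent doses of rituximab will be given on the same day as BI-1206".

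For lymphocyte counts above 25 x 10^9/L, Section 5.9.2 recommends a steroid before rituximab and asks that a slower first infusion and a Week 1 split be considered, with the split given as "rituximab 100mg IV Day 1 (Week 1 only) followed by rituximab" 375 mg/m² less 100 mg on Day 2. Section 6.2.11 repeats it: "dosing may be split over two days during the first week, i.e. rituximab 100mg IV Day 1 (Week 1 only"). It also requires the Sponsor and Chief Investigator to agree the rate and "any split dosing requirements and communicate these to the investigator site before the start of treatment".

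The Arm 2 pharmacokinetic plan (8.3.1.3) takes a BI-1206 sample "at 24 hours after the BI-1206 infusion (before the rituximab infusion) and at 72 hours after the BI-1206 infusion at Week 1". The Table 5 footnote, "If rituximab is given on Day 1, this sample will be at the end of rituximab infusion instead", is attached to the Week 4 four-hour sample only.

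**The concern.** Two dosing sections give a different Week 1 rituximab day from the schedule, and nothing marks the difference as intended. A site following 5.9.2 or 6.2.11 literally would give the first rituximab on the first BI-1206 day. It would do so only in patients for whom the protocol wants extra precaution against infusion reactions and cytokine release. Patients on the standard schedule would keep the two first exposures on separate days.

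Section 2.2.6 reports rituximab infusion-related reactions in more than half of patients, mostly at the first infusion. Section 2.2.8 expects reactions to BI-1206 as well. Causality in relation to each antibody is part of the primary safety endpoint for Arm 2 (3.1.1), and 6.2.5.6 and 6.2.11.2 consider withdrawal agent by agent. With both first doses on one day, that attribution is less clear.

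**Working it through.** The plan states no figure on this point, so the check is a comparison of texts with some supporting arithmetic.

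**Week 1 under each reading**

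| Source and reading | Day 1 | Day 2 | Day 3 | Infusion days |
|---|---|---|---|---|
| 5.2.2 and note (h), no split | BI-1206 | rituximab, full dose | none | 2 |
| 5.9.2 and 6.2.11, days of the trial week | BI-1206 and rituximab 100 mg | rituximab remainder | none | 2 |
| 5.9.2 and 6.2.11, days of the split, start set by 5.2.2 | BI-1206 | rituximab 100 mg | rituximab remainder | 3 |

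The second row contradicts the first. The third agrees with 5.2.2, but only if the printed labels are changed. Usage elsewhere favours the second row: in the Figure 3 and Table 5 footnotes, Day 1 rituximab means rituximab on the BI-1206 day. No Arm 2 text puts rituximab on Day 3 of a week. The column positions in the Figure 3 grid are not relied on.

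**Length of the 100 mg part.** Section 6.2.11 starts at 50 mg/h and allows 50 mg/h steps every 30 minutes.
- Fastest: 50 x 0.5 = 25 mg; 100 x 0.5 = 50 mg; the last 25 mg at 150 mg/h takes 25/150 = 0.17 h. Total 0.5 + 0.5 + 0.17 = 1.17 h.
- Held at 50 mg/h: 100/50 = 2.0 h.
- It takes longer at the reduced rate that the protocol asks sites to consider.

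Section 2.2.6 places most reactions in the first one to two hours of the first infusion, so the 100 mg part spans that window.

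**Would infusion length rule out Day 1 in practice?** The BI-1206 rate steps are in the pharmacy guidelines, not the protocol. Assuming 50 mg/h steps every 30 minutes from 50 mg/h, the first infusion takes 1.17 h (100 mg) to 3.75 h (800 mg). Suppose the site waits out the minimum 4-hour watch after BI-1206 (5.9.2), gives rituximab 100 mg at the fastest printed rate and then monitors for 0.5 h:
- 100 mg: 1.17 + 4 + 1.17 + 0.5 = about 6.8 h
- 800 mg: 3.75 + 4 + 1.17 + 0.5 = about 9.4 h

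If BI-1206 stays at 50 mg/h, its infusion alone takes 100/50 = 2 h to 800/50 = 16 h. The literal reading is therefore workable in many cases, and infusion length would not reliably expose the error. The gap between the two antibodies could fall from about a day to about 4 h, or less, since no text makes the site wait out the watch.

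**Pharmacokinetics.** Table 5 gives 5 + 1 + 1 + 5 = 12 samples; 12 x 6 mL = 72 mL, as printed. On the literal reading the Week 1 24-hour sample, 1 of 5 that week, would follow rituximab 100 mg. Section 8.3.1.3 has its own split-dosing provision (up to 18 time points; 18 x 6 mL = 108 mL, as printed) and leaves adjusted sample times to the laboratory manual. This effect is therefore minor.

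**The case against.** The best defence is that Day 1 and Day 2 are simply the two days of the split. Section 6.2.11 introduces them straight after speaking of two days, and with 5.2.2 fixing the start there would be no conflict, only loose labels. The split is optional, and 6.2.11 requires the Sponsor and Chief Investigator to agree it before treatment, so a site does not choose the days alone. Both points soften the concern. Neither removes it: the text does not say the days are relative, rituximab Day 1 means the BI-1206 day elsewhere, and those agreeing the split work from wording that prints Day 1.

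The objection is right on several stronger inferences that a reader might draw:
- **That the separate days are themselves the stated safety measure.** In 5.2.2 the precaution is the slow infusion, and the separate days follow from it.
- **That DLT decisions are compromised.** Section 3.3 counts events related to either antibody and excludes Grade 3 infusion reactions.
- **That agent-by-agent withdrawal is triggered at once.** In 6.2.5.6 and 6.2.11.2 the advice to consider withdrawing one agent applies when a further reaction prevents the next full dose.
- **That splitting BI-1206 creates a second contradiction.** The protocol does not say that BI-1206 split days are consecutive, and it fixes the order of the two antibodies. The rituximab day is missing detail there, not conflicting text.

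**Conclusion.** The point holds as an inconsistency in a dosing instruction. Sections 5.9.2 and 6.2.11 either place the first rituximab on the first BI-1206 day, against 5.2.2 and note (h), or label the days wrongly. Both need the same correction.

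The effect is confined to Arm 2 patients above the lymphocyte threshold whose Week 1 rituximab is split. For them, on the literal reading, the early rituximab reaction window moves onto the first BI-1206 day and attribution is blurred. A reader might want a count of affected patients. The documents give neither the distribution of lymphocyte counts nor how often the split would be used, so none is offered. The timings assume the printed rituximab rates and, for BI-1206, an assumed rate step. The conclusion depends on neither.

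**What to change.** In 5.9.2 and 6.2.11, print the split as: *rituximab 100 mg IV on Day 2 and the remainder of 375 mg/m² on Day 3 (Week 1 only)*. Add the same exception to 5.2.2 and to note (h), so that all four places agree. The 24-hour BI-1206 sample then stays before rituximab, and dosing still finishes before the Week 2 dose on Day 8.

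The cost is wording in four places and one extra infusion day in Week 1 (3 days instead of 2) for patients whose rituximab is split. If the sponsor does intend rituximab on Day 1 for these patients, the protocol should say so as an explicit exception, with the reason. No new rule for later weeks or for split BI-1206 is needed to settle this point.
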